4.6 PATIENT, TREATMENT, STUDY, AND SITE DISCONTINUATION

4.6.1 Patient Discontinuation

Patients have the right to voluntarily withdraw from the study at any time for any reason. In addition, the investigator has the right to withdraw a patient from the study at any time. Reasons for withdrawal from the study may include, but are not limited to, the following:

- Patient withdrawal of consent at any time
- Any medical condition that the investigator or Sponsor determines may jeopardize the patient's safety if he or she continues in the study
- Investigator or Sponsor determines it is in the best interest of the patient
- Patient non-compliance, specifically defined as: refusal to allow for serum draws for antibodies; failure to adhere to study visit schedule; failure to comply with GH administration by giving less than 85% of daily injections over each 3-month interval

Nutropin AQ (Somatropin [rDNA origin])—Genentech, Inc. 33/Protocol ML29543, Version 2

• Development of growth failure with velocity decrease to below pretreatment velocity

Every effort should be made to obtain information on patients who withdraw from the study. The primary reason for withdrawal from the study should be documented on the appropriate eCRF. However, patients will not be followed as part of the study for any reason after consent has been withdrawn. Patients who withdraw from the study prematurely will not be replaced.

4.6.2 Study Treatment Discontinuation

Patients who experience a protocol-defined adverse event may be discontinued from treatment (see Section 5.1.1). Patients who discontinue study treatment prematurely will be asked to return to the clinic for an early discontinuation visit and may undergo final study assessments. The primary reason for premature study treatment discontinuation should be documented on the appropriate eCRF. Patients who discontinue study treatment prematurely may remain in the study and continue to be followed per the schedule of assessments for sample collection, reporting of adverse events, and height and weight measurements.

4.6.3 Study and Site Discontinuation

The Sponsor has the right to terminate this study at any time. Reasons for terminating the study may include, but are not limited to, the following:

- The incidence or severity of adverse events in this or other studies indicates a potential health hazard to patients
- Patient enrollment is unsatisfactory

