6.3.1 Primary Endpoint

The primary endpoint for this study is the proportion of patients who develop anti-GH antibodies after *initiating* treatment with Nutropin AQ v1.1.

6.3.2 Secondary Endpoints

The secondary endpoints for this study are as follows:

- Proportion of patients who exhibit growth attenuation (defined as initial growth response greater than pretreatment velocity followed by reduction in growth response to below the pretreatment velocity in the subsequent 6- to 12-month treatment period or reaching ≤2 cm per year)
 - Cross tabulation between growth attenuation status (i.e., with or without) and anti-GH antibody status (i.e., positive or negative) will be provided for any

Nutropin AQ (Somatropin [rDNA origin])—Genentech, Inc.

48/Protocol ML29543, Version 2

antibody and for neutralizing anti-GH antibody, respectively, at each visit. Similar tables will also be provided for patients who had at least one positive anti-GH antibody (anti-GH antibody and neutralizing antibody, respectively) at any follow-up visit against those who never developed antibody after treatment.

- Proportion of patients with neutralizing antibody among those who had positive anti-GH antibody
 - This analysis will be summarized by visit, as well as *cumulatively*, for patients who had detectible anti-GH antibody at any post-baseline visit, as well as those who *remained negative throughout the study*.
- Annualized 6- and 12-month growth velocities and height SDS will be summarized separately for patients who were anti-GH antibody-positive at any post-baseline follow-up visit and those who were anti-GH antibody-negative at all visits (including baseline). Graphic displays of the individual patient growth patterns along with the longitudinal antibody profile over the course of the study will be prepared. Patients who enter puberty during the study period will be included up to the last visit at which they were determined to be prepubertal.

Additional analyses deemed appropriate for assessing immunogenicity will be described in the Statistical Analysis Plan.

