4.4.1 Primary Outcomes Endpoint

The primary endpoint for this study is the proportion of patients who develop anti-GH antibodies (i.e., with positive anti-GH antibody screening assay result) after initiating treatment with Nutropin AQ v1.1.

Among all patients with at least one post-baseline screening assay result, the number and percentage of patients who have at least one positive anti-GH antibody screening assay result at any post-baseline visit will be presented. The Clopper-Pearson exact 95% Cls for the percentage will also be provided.

An anti-GH antibody screening assay result is considered positive if the titer is \geq 1.0 mg/L.

4.4.2 Secondary Outcomes Endpoints

The secondary endpoints for this study are as follows:

- Proportion of patients who exhibit growth attenuation is defined as
 - (1) initial growth response greater than pretreatment velocity followed by reduction in growth response to below the pretreatment velocity in the subsequent 6- to 12month treatment period

or

(2) reaching \leq 2 cm per year at any scheduled visit: Month 3, 6, 9, or 12

Please note that for criteria (1), the initial growth response occurs as early as Month 3 and growth attenuation status at post-baseline visit will be evaluated at Months 6, 9, or 12.

The growth response is based on the annualized growth velocity defined as (height - baseline height)/ (date of height assessment – date of baseline)*365.25 at any post-baseline visit.

Pretreatment growth velocity is defined as (Baseline height – last historical height) / (date of baseline – date of last historical height)*365.25

Growth attenuation status at post-baseline visit Tk (=Month 6, Month 9 or Month 12 for k=6, 9, or 12) will be classified as follows:

Yes: If growth velocity at Tk< pretreatment growth velocity and there is Tj < Tk with growth velocity at Tj > pre-treatment growth velocity, for j<k, and k=6, 9, or 12 or growth velocity \leq 2 cm per year at any scheduled visit: Month 3, 6, 9, or 12 **No:** Otherwise.

Nutropin AQ (Somatropin [rDNA origin])—Genentech, Inc. 9/Statistical Analysis Plan ML29543 • 2x2 cross tabulation (with frequencies and percentages) of growth attenuation status (yes or no) and anti-GH antibody status (positive or negative) will be provided for each antibody assay at each visit (Month 6, 9, and12).

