4.7 MISSING DATA

Missing data will not be imputed for efficacy outcome measures. All available assessments will be reported with associated number of observations. If a patient discontinues study medication before the end of the 1-year treatment period, their growth rate will be computed for the last 3-month interval visit and used in the calculation of mean growth for that time interval only.

Nutropin AQ (Somatropin [rDNA origin])—Genentech, Inc. 13/Statistical Analysis Plan ML29543

There are two criteria for defining growth attenuation: (1) initial growth response greater than pretreatment velocity followed by reduction in growth response to below the pretreatment velocity in the subsequent 6- to 12-month treatment period, or (2) reaching \leq 2 cm per year at any scheduled visit: Month 3, 6, 9, or 12.

For criteria (1), if the pretreatment velocity is missing then growth attenuation is missing. Otherwise,

- 1. If patient discontinued < month 3, the growth attenuation will be missing because the initial growth response cannot be determined for criteria (1).
- 2. If patient discontinued \geq month 3 and < month 6, then:
 - a. If the height on Month 3 is missing, the growth attenuation will be missing because the initial growth response cannot be determined.
 - b. If the height on Month 3 is non-missing, the initial growth response can be determined but the growth attenuation cannot be determined because there is no Month 6 visit to determine the reduction in growth response to below the pretreatment velocity.
- 3. If patient discontinued ≥ month 6, the growth attenuation will be calculated based on the original definition.

For safety analyses, incomplete onset dates for adverse events and concomitant medications will be imputed according to the following algorithm:

- If the day is missing, the 1st of the month will be used.
- If the day and month are missing, January 1st will be used.

In cases where the imputation of the start/onset date leads to adverse events or concomitant medications occurring before treatment start, the start date will be set to the treatment start date.

Incomplete end dates for non-ongoing adverse events or concomitant medications will be imputed according to the following algorithm:

- If the day is missing, the last day of the month will be used.
- If the day and month are missing, December 31st will be used.

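### Growth attenuation is classified from heights with no on-treatment condition, so growth after stopping the drug can, in limited circumstances, be counted as attenuation within the treatment period

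*Protocol*

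**What the plan says.** - **Follow-up off drug.** Protocol 4.6.2: "Patients who discontinue study treatment prematurely may remain in the study and continue to be followed per the schedule of assessments". Heights are among the measurements that continue.
- **Endpoint.** Protocol 6.3.2 defines attenuation as an initial response above pretreatment velocity "followed by reduction in growth response to below the pretreatment velocity in the subsequent 6- to 12-month treatment period", or a velocity of 2 cm per year or less.
- **Velocity.** SAP 4.4.2 uses "annualized growth velocity defined as (height - baseline height)/ (date of height assessment" minus the baseline date), times 365.25, at any post-baseline visit. It is cumulative from baseline, not visit to visit.
- **Criterion 1.** SAP 4.4.2 returns *Yes* at Month 6, 9 or 12: "If growth velocity at Tk< pretreatment growth velocity and there is Tj < Tk with growth velocity at Tj > pre-treatment growth velocity".
- **Criterion 2.** Velocity at or below "2 cm per year at any scheduled visit: Month 3, 6, 9, or 12".
- **Population and cut-offs.** SAP 4.1.5 requires one dose and one post-baseline assessment. SAP 4.4 ends a child's growth data at puberty and sets no matching limit at the last dose.
- **Discontinuation.** For criterion 1, SAP 4.7 makes status missing if the child discontinued before Month 3. From Month 3 to before Month 6 it is missing or undeterminable; where the Month 3 height exists, the reason given is that no Month 6 visit exists. After that: "If patient discontinued ≥ month 6, the growth attenuation will be calculated based on the original definition". A separate sentence, for children who stop study medication, limits their contribution to mean growth to the last 3-month interval.

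**The concern.** Attenuation is the trial's marker that antibodies are blocking the drug. A child who has stopped the drug may slow for a reason unrelated to antibodies. The plan keeps such children on the height schedule, and nothing in the attenuation rule asks whether the child was still being treated. The words treatment period in the endpoint are not turned into an operational condition.

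SAP 4.7 does not settle the matter:

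- It does not say whether discontinued means leaving the study or stopping the drug.
- Its reason in rule 2b, that there is no Month 6 visit, is untrue for a child who stops the drug and stays under Protocol 4.6.2.
- It gives no discontinuation rule for the 2 cm/yr criterion.
- Its mean-growth sentence does not mention attenuation status or the individual plots, and does not clearly cover the difference between 6- and 12-month velocities.

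The plan already removes one cause of growth change that has nothing to do with antibodies (puberty) and leaves this one in. The stake is the clinical-impact objective. Protocol 3.3.3 calls attenuation due to neutralizing antibodies rare, so one or two misclassified children could be much of what the cross-tabulations show.

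**Working it through.** **The plan's own figure.** The documents give no figure for attenuation. The only design calculation is the Clopper-Pearson interval for the primary endpoint. With n = 50 and 25 positive it reproduces as 35.53% to 64.47%. I use the same method for the intervals below.

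**Inputs.** The velocity formula and criteria come from SAP 4.4.2. Enrolment of 80, dropout of 10–15% and the puberty allowance of 10% come from Protocol 6.1. The documents give no velocities except the 2 cm/yr cut-off, so all velocities here are assumptions: pretreatment 4 or 5 cm/yr, on-drug 4.5 to 10.

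**Formula.** Suppose a child stops at month s, with velocity Von before and Voff after. The SAP velocity at month t is

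V(t) = [s × Von + (t − s) × Voff] / t.

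Criterion 1 then needs V(t) < Vpre, that is,

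Voff < (t × Vpre − s × Von) / (t − s).

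For a Month 6 stop read at Month 12 this becomes Voff < 2 × Vpre − Von.

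**Return to the pretreatment rate.** With Vpre 4, Von 8 and Voff 4 after Month 6, V(12) = (6 × 8 + 6 × 4)/12 = 6.0. More generally, if the cumulative velocity at stopping is above Vpre and Voff equals Vpre, the average stays above Vpre. Criterion 1 is not met.

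**How far growth must fall.** Off-drug velocity (cm/yr) must lie below these limits for a *Yes* at Month 12, with Vpre = 5:

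| Von | Stop Month 3* | Stop Month 6 | Stop Month 9 |
|---|---|---|---|
| 5.5 | 4.83 | 4.5 | 3.5 |
| 6 | 4.67 | 4.0 | 2.0 |
| 7 | 4.33 | 3.0 | not possible |
| 9 | 3.67 | 1.0 | not possible |
| 10 | 3.33 | 0 | not possible |

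*Only if SAP 4.7 rule 2 is read as not covering a child who stops the drug and stays. Not possible means that height loss would be needed.

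With Vpre = 4 and a Month 6 stop, the limits are 3.5, 3.0, 2.0 and 0 for Von of 4.5, 5, 6 and 8.

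**A false Yes.** Take Vpre 5, Von 6 to Month 6 (3.0 cm) and Voff 3.5 for six months (1.75 cm). Then V(6) = 6 and V(12) = 4.75, which is below 5: *Yes*. Growth on drug never slowed. With heights cut at the last dose, the child has V(6) = 6 > 5: *No*.

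**Criterion 2.** For a Month 6 stop read at Month 12, (Von + Voff)/2 ≤ 2 requires Voff ≤ 4 − Von. With any positive off-drug growth, Von must be below 4 cm/yr.

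**Velocity displays.** Take Von 9 to Month 6 and Voff 4 after. V(6) = 9 and V(12) = 4.5 + 2.0 = 6.5, a difference of −2.5 cm/yr that comes wholly from stopping. If the mean-growth sentence does not apply, one such child lowers a group's mean difference by 2.5/n: 0.08 cm/yr among 30 children (50% of 60) or 0.21 among 12 (20% of 60).

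**Exit-visit height.** Use the same 5, 6 and 3.5 with a Month 6 stop and a height 28 days later. Off-drug growth is 3.5 × 28/365.25 = 0.27 cm, so V = 3.27/0.577 = 5.7, still above 5.

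**Effect on the proportion.** Growth-evaluable children: 80 × (1 − 0.15 − 0.10) = 60.

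| False cases of 60 | Percentage | 95% interval |
|---|---|---|
| 0 | 0 | 0 to 6.0% |
| 1 | 1.7% | 0.04 to 8.9% |
| 2 | 3.3% | 0.4 to 11.5% |

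**The case against.** The strongest reply is that the SAP's own formula largely protects the endpoint. Averaging from baseline dilutes anything that happens after stopping. A reader might infer that stopping the drug by itself reproduces the attenuation pattern; the formula does not support that. A fall below the child's own untreated rate is needed, and no document says that such a fall occurs. This stands, and it limits the point to modest responders and early stops.

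The other arguments:

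- **Early stops may already be out.** If discontinued includes stopping the drug, SAP 4.7 rules 1 and 2 remove stops before Month 6 from criterion 1, where dilution is weakest. This stands only on that reading, and rule 2b's stated reason points to children who have left the study.
- **The number affected may be zero.** Staying is optional, and Protocol 4.6.1 lists poor compliance and velocity below the pretreatment rate among possible reasons for withdrawal from the study. A reader might take the projected 10–15% dropout (8 to 12 of 80) as the count at risk. It counts dropouts, not children who stop and stay, so it does not support that.
- **Such a child would be visible.** The study is descriptive, SAP 4.6.1 lists drug administration, and SAP 4.6.3 presents individual drug concentration, growth and antibody profiles. That helps a careful reader of the listings but does not correct the cross-tabulations.
- **The exit-visit height is immaterial.** In the example above it is. The fix therefore allows for it.
- **Off-drug heights are useful to display.** Agreed. They should stay in the listings and plots, with the last dose marked.

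**Conclusion.** The gap is real and its reach is limited. As written, the SAP can count growth after the last dose as attenuation in an endpoint worded as slowing within the treatment period, and its discontinuation rules do not say which kind of discontinuation they mean. A false *Yes* on criterion 1 needs off-drug growth clearly below the pretreatment rate: for a Month 6 stop read at Month 12, below twice the pretreatment rate minus the on-drug rate. Criterion 2 is harder still to meet this way. The 12-month velocity and the individual plots can be pulled down without so large a fall.

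Each false case adds about 1.7 percentage points at n = 60. All velocities are illustrative, and the number of children who stop and stay is unknown. A reader might infer that the immunogenicity result itself is at risk. It is not: the primary endpoint uses antibody results, not heights, and only descriptive secondary endpoints are affected. The change is worth making because true events are expected to be rare and the correction is cheap.

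**What to change.** 1. **SAP 4.4 and 4.4.2, beside the puberty cut-off.** Suggested text: *For growth attenuation (both criteria) and for the 6- and 12-month growth velocity and height SDS summaries, including the difference between the two velocities, heights taken after the last dose of study drug plus a stated allowance covering the exit visit (for example 28 + 3 days) are not used.*
2. **SAP 4.7.** Define discontinued as treatment discontinuation for the attenuation rules, reword rule 2b so that it does not depend on the absence of a Month 6 visit, and make clear that the height cut-off also governs the 2 cm/yr criterion.
3. **Displays.** Keep later heights in the listings, and show them in the individual growth and antibody plots with the last-dose date marked.
4. **Unchanged.** Antibody samples taken after the last dose stay in the primary endpoint.

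On-drug attenuation is still captured, because heights up to the last dose and within the allowance remain. The cost is a few sentences and one date filter on the last treatment date, which SAP 4.6.1 already needs for exposure. The downside is that a few off-treatment heights leave the growth tables.

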5.1 SAFETY PLAN

Patient safety will be monitored through physical exams and incidence or severity of adverse events and serious adverse events.

5.1.1 Adverse Events That May Lead to Discontinuation of Treatment with Nutropin AQ v1.1

Management of specific adverse events should follow the information provided in the USPI for Nutropin AQ, published guidelines, and standard of care practices in the monitoring of patients receiving rhGH therapy.

Events that may lead to discontinuation of Nutropin AQ v1.1 include, but are not limited to, the following:

- Papilledema by fundoscopy
- Somatropin-induced intracranial hypertension
- Evidence of recurrent or new malignancy
- New or recurrent event of slipped capital femoral epiphysis (SCFE) or avascular necrosis (AVN)
- Diabetes mellitus
- Pancreatitis
- New scoliosis or significant scoliosis progression
- Anaphylactic reactions/severe hypersensitivity
- Acute critical illness requiring intensive care hospitalization

5.2 SAFETY PARAMETERS AND DEFINITIONS

Safety assessments will consist of monitoring and recording adverse events, including serious adverse events and non-serious adverse events.

Certain types of events require immediate reporting to the Sponsor, as outlined in Section 5.4.

5.2.1 Adverse Events

According to the ICH guideline for Good Clinical Practice, an adverse event is any untoward medical occurrence in a clinical investigation subject administered a pharmaceutical product, regardless of causal attribution. An adverse event can therefore be any of the following:

• Any unfavorable and unintended sign (including an abnormal laboratory finding), symptom, or disease temporally associated with the use of a medicinal product, whether or not considered related to the medicinal product

Nutropin AQ (Somatropin [rDNA origin])—Genentech, Inc. 35/Protocol ML29543, Version 2
- Any new disease or exacerbation of an existing disease (a worsening in the character, frequency, or severity of a known condition), except as described in Section 5.3.5.9
- Recurrence of an intermittent medical condition (e.g., headache) not present at baseline
- Any deterioration in a laboratory value or other clinical test (e.g., ECG, X-ray) that is associated with symptoms or leads to a change in study treatment or concomitant treatment or discontinuation from study drug
- Adverse events that are related to a protocol-mandated intervention, including those that occur prior to assignment of study treatment (e.g., screening invasive procedures such as biopsies)

5.2.2 Serious Adverse Events (Immediately Reportable to the Sponsor)

A serious adverse event is any adverse event that meets any of the following criteria:

- Is fatal (i.e., the adverse event actually causes or leads to death)
- Is life threatening (i.e., the adverse event, in the view of the investigator, places the patient at immediate risk of death)
 - This does not include any adverse event that had it occurred in a more severe form or was allowed to continue might have caused death.
- Requires or prolongs inpatient hospitalization (see Section 5.3.5.10)
- Results in persistent or significant disability/incapacity (i.e., the adverse event results in substantial disruption of the patient's ability to conduct normal life functions)
- Is a congenital anomaly/birth defect in a neonate/infant born to a mother exposed to study drug
- Is a significant medical event in the investigator's judgment (e.g., may jeopardize the patient or may require medical/surgical intervention to prevent one of the outcomes listed above)

The terms "severe" and "serious" are not synonymous. Severity refers to the intensity of an adverse event (e.g., rated as mild, moderate, severe, or life-threatening; see Section 5.3.3); the event itself may be of relatively minor medical significance (such as severe headache without any further findings).

Severity and seriousness need to be independently assessed for each adverse event recorded on the eCRF.

Serious adverse events are required to be reported by the investigator to the Sponsor immediately (i.e., no more than 24 hours after learning of the event; see Section 5.4.2 for reporting instructions).

Nutropin AQ (Somatropin [rDNA origin])—Genentech, Inc. 36/Protocol ML29543, Version 2

5.2.3 Non-Serious Adverse Events of Special Interest (Immediately Reportable to the Sponsor)

Non-serious adverse events of special interest are required to be reported by the investigator to the Sponsor immediately (i.e., no more than 24 hours after learning of the event; see Section 5.4.2 for reporting instructions). Those adverse events of special interest for this study include the following:

- Cases of potential drug-induced liver injury that include an elevated ALT or AST in combination with either an elevated bilirubin or clinical jaundice, as defined by Hy's law (see Section 5.3.5.7)
- Suspected transmission of an infectious agent by the study drug, as defined below
 - Any organism, virus, or infectious particle (e.g., prion protein transmitting transmissible spongiform encephalopathy), pathogenic or non-pathogenic, is considered an infectious agent. A transmission of an infectious agent may be suspected from clinical symptoms or laboratory findings that indicate an infection in a patient exposed to a medicinal product. This term applies only when a contamination of the study drug is suspected.

